#### 9.2 Inclusion Criteria

The participants have to meet all of the following criteria to be eligible to enter the study:

- 1) Willing and able to provide informed consent
- 2) Male or female and aged 18 years or above
- 3) Volunteers able to read and understand English
- 4) A personal history of atopic dermatitis

The diagnosis of AD history will be set according to UK working party 1994 (37).

#### 9.3 Exclusion Criteria

Participants meeting any of the following criteria will not be permitted to enter the study:

- 1) Eczema on the volar forearms requiring anti-inflammatory treatment
- Possible allergy to ingredients in the study medications.
- 3) Any serious current medical condition which, in the opinion of the Investigator, may interfere with the evaluation of the results or may be contraindicated by the use of the test medications
- 4) Use of any concomitant medication that may interfere with the study related activities or assessment of efficacy, as judged by the Investigator
- 5) Use of any topical product, including cosmetic leave-on products on the volar forearms, within 1 week prior to, and throughout the study
- 6) Female participant who, according to the participant, is pregnant or breast-feeding, or plans to become pregnant during the course of the study
- 7) Any participant-related factor suggesting potential poor compliance with study procedures (e.g. psychiatric disorders, history of alcohol or substance abuse), as judged by the Investigator
- 8) Enrolment in any interventional study or use of an investigational drug within 3 months prior to the screening visit. Cosmetic studies on emollient use are allowed and the wash out period is 7 days, as with any emollient used
- 9) Volunteers judged by the PI to be inappropriate for the trial.

Confidential Page 31 of 65

Version: Version 3.0 Date: 15 August 2019

#### 9.4 Restrictions

- Medications Prohibited >28 Days Prior to Baseline/Day 1 and throughout the study
  - Use of systemic (oral, parenteral) corticosteroids prohibited less than 3 months prior to baseline/day 1 and throughout the study

Sponsor: ACO Hud Nordic AB

EudraCT No.: 2018-002945-12

Study Code: Novum ACO-CT-2018-01

- Medications Prohibited 28 Days Prior to Baseline/Day 1 and throughout the study
  - Use of TCS, or TCI, anywhere on the body.
  - o Inhaled glucocorticoids of low to moderate doses for treatment of asthma are allowed
  - Use of systemic immunosuppressive agents, including but not limited to, methotrexate, ciclosporin, azathioprine, hydroxychloroquine, and mycophenolate mofetil.
  - Tanning bed use, or light therapy Ultraviolet (UV), Ultraviolet B (UV-B), psoralen–UV-A [PUVA]).
  - Use of topical retinoids.
- Medications Prohibited 14 Days Prior to Baseline/Day 1 and throughout the study
  - Use of systemic antibiotics.
  - o Use of topical antihistamines anywhere on the body.
- Medications Prohibited 7 Days Prior to Baseline/Day 1 and throughout the study
  - Use of topical antibacterial medications or products, including antibacterial soaps, bleach baths, topical sodium hypochlorite-based products anywhere on the body.
  - Systemic sedating antihistamines (eg, hydroxyzine or diphenhydramine or other sedating antihistamines).
  - Use of systemic non-sedating antihistamines in a nonstable (eg, escalating or decreasing, or as needed) regimen. Subjects on a stable non-sedating systemic antihistamine regimen with ≤7 days of consistent use prior to Visit 1 are permitted to continue but must not alter or stop their regimen during the study.
  - Use of bland (non-medicated) emollients, moisturisers or sunscreen on the test areas, within 7 days prior to Visit 1. Use of bland (non-medicated) emollient(s) is permitted during the study to manage dry skin in areas surrounding but not on or overlapping the test areas.
- Medications prohibited from Baseline/Day 1 and throughout the study
  - Use of vasoactive drugs in a non-stable (eg, escalating or decreasing, or as needed) regimen including: metaraminol, adrenaline/epinephrine, noradrenaline/norepinephrine, phenylephrine, dobutamine, dopamine, dopexamine, oxymetazoline.
  - Peroral anti-fungal medication
  - Topical anti-fungal creams on the test areas

Confidential Page 32 of 65

Version: Version 3.0 Date: 15 August 2019

#### 9.5 Screening failure

All individuals who sign the consent form and either (1) withdraw their participation before the first assessment/procedure, (2) fail to meet all of the eligibility criteria and/or (3) for technical or logistical reasons do not participate in the first assessment session will be considered a "screening failure."

Sponsor: ACO Hud Nordic AB

EudraCT No.: 2018-002945-12

Study Code: Novum ACO-CT-2018-01

#### 9.6 Removal of Participants from Treatment or Assessment

Participants are free to discontinue their participation in the study at any time. Withdrawal from the study will not affect or prejudice the participant's further care or treatment. Participants may be withdrawn from study treatment and assessments at any time, if deemed necessary by the Investigator.

Potential reasons for withdrawal of participants from this study are:

- If a participant decides to withdraw from the study (including if the participant withdraws informed consent)
- Intercurrent illness
- If the participant uses any prohibited concomitant medication or treatments listed in Section 9.4, at the discretion of the Investigator
- If the participant experiences an unacceptable AE
- If the participant is lost to follow-up

The reason and date the participant is withdrawn from the study will be documented in the CRF (e.g. lost to follow-up, consent withdrawn, incorrect enrolment, AEs, etc.). If a participant is withdrawn from further treatment with the investigational creams, the Investigator should complete the study termination page of the CRF. All AEs should be followed up in accordance with Section 12.2.

If a participant is withdrawn from the study, all data collected until the time of withdrawal will be used in the analyses.

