#### 12 ADVERSE EVENTS

#### 12.1 Definitions

#### 12.1.1 Adverse Event

Any untoward medical occurrence in a participant or clinical trial subject administered a medicinal product and which does not necessarily have a causal relationship with this treatment.

Comment: An AE can therefore be any unfavourable and unintended sign (including an abnormal laboratory finding), symptom, or disease temporally associated with the use of an investigational medicinal product, whether or not considered related to the investigational medicinal product.

If eczema appears on a study area or the untreated control area, the participant should note the date in the diary and immediately contact the Investigator in order to have the eczema investigated. The participant should continue to treat the eczema with the randomised cream until he/she has seen the Investigator. The Investigator judges if the eczema should be documented as an AE and if the participant will continue in the study. The participant will then be instructed to continue his/her treatment with the randomised cream or discontinue the study.

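### Protocol 9.6 and 12.1.1 do not say that a participant whose cream is stopped, or who has one unfit area, keeps the Day 29 and Day 31 assessments, so removal by the investigator loses the primary value at all four areas

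*Protocol*

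**What the plan says.** **Eczema on an area (Protocol 12.1.1).** The rule applies "If eczema appears on a study area or the untreated control area". The investigator then decides: "The Investigator judges if the eczema should be documented as an AE and if the participant will continue in the study". Two outcomes follow: "The participant will then be instructed to continue his/her treatment with the randomised cream or discontinue the study".

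**Withdrawal (Protocol 9.6).** The unit is the participant, and treatment and assessments are named together: "Participants may be withdrawn from study treatment and assessments at any time, if deemed necessary by the Investigator". Stopping the creams leads to a form: "If a participant is withdrawn from further treatment with the investigational creams, the Investigator should complete the study termination page of the CRF". After withdrawal, "all data collected until the time of withdrawal will be used in the analyses".

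**Treating the eczema.** Protocol 9.4 prohibits the following during the study: "Use of TCS, or TCI, anywhere on the body". Protocol 9.6 lists as a possible reason for withdrawal: "If the participant uses any prohibited concomitant medication or treatments listed in Section 9.4, at the discretion of the Investigator". Protocol 10.6 adds that medication needed for safety and well-being may be given at the investigator's discretion, and that this may lead to withdrawal.

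**What the primary analysis needs.** The primary outcomes are Day 31 minus Day 29 changes in TEWL and redness (Protocol 11.1, SAP 6.1). TEWL is read on Days 1, 29 and 31 only (SAP 6.4), and missing data are not replaced (Protocol 13.1.2, SAP 7.6). The FAS is all randomised participants with a diagnosed history of AD (Protocol 13.1.1, SAP 5). The model has treatment as a factor, subject as a random effect and Day 29 as a covariate (SAP 7.1).

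**The concern.** In a within-participant trial with four areas, a local problem belongs to an area, while the withdrawal rule belongs to the participant. The text sets out no step between carrying on and leaving. This is plainest for the untreated area, where there is no cream to stop or continue.

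Keeping data up to withdrawal does not help the primary analysis. Both the Day 29 and the Day 31 reading are needed, so a participant removed before Day 31 contributes no primary value from any area. Three sound areas can be lost with one affected area, including from contrasts in which the affected area plays no part.

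At stake are some avoidable loss of precision and possible selection of who remains, since those who flare may be the ones removed. The documents give neither the frequency nor the direction of such selection.

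**Working it through.** **1. Is there a stated route to keep the assessments?**

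| Situation | Where | What is stated |
|---|---|---|
| Eczema on a test or untreated area | Protocol 12.1.1 | Continue the randomised cream, or leave the study; investigator decides |
| Withdrawn from the creams | Protocol 9.6 | Complete the study termination page |
| Prohibited medication used | Protocol 9.6 | Withdrawal possible, at discretion |
| Necessary medication given | Protocol 10.6 | Allowed; withdrawal possible |
| Cream applied on under 75% of days | Protocol 10.7 | Excluded from the per-protocol population |

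Staying in after treatment is allowed. Continued Day 29 and Day 31 assessments after a cream stop, or on the remaining areas when one is unfit, are neither provided for nor forbidden.

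**2. Which contrasts survive if fit areas are kept?** The contrasts are test versus untreated, test versus Miniderm 20% and test versus Diprobase. Assume the affected area is equally likely to be any of the four.

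| Affected area | Contrasts kept of 3 |
|---|---|
| Test cream | 0 |
| Untreated | 2 |
| Miniderm 20% | 2 |
| Diprobase | 2 |

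The total is 6 of 12, so each contrast keeps 1/2 of affected participants. If both areas on a forearm are unfit, there are six possible treatment pairs. The three that include the test cream keep 0 of 3 contrasts, and the other three keep 1 of 3. The total is 3 of 18, so each contrast keeps 1/6.

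**3. Effect on the standard error.** Let f be the share of participants who would be removed this way. It is not in the documents. I assume 4–20%, where 20% is the plan's whole dropout allowance (40/(1 − 0.20) = 50, Protocol 13.2) and so a ceiling. On complete pairs, relative to no loss:

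- participant removed: 1/√(1 − f)
- fit areas kept, one area unfit: 1/√(1 − f/2)
- fit areas kept, both areas on a forearm unfit: 1/√(1 − 5f/6)

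| f | Removed | Kept, one unfit | Kept, two unfit |
|---|---|---|---|
| 4% | 1.021 | 1.010 | 1.017 |
| 10% | 1.054 | 1.026 | 1.044 |
| 20% | 1.118 | 1.054 | 1.095 |

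These ratios depend on neither N nor the SD. A generalised least squares check with equal correlation between areas (0 to 0.9), one area missing and f = 10% gives 1.013 to 1.017. The random-subject model therefore recovers somewhat more than the complete-pairs figure of 1.026.

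**4. The same in power, for test versus no treatment.** Inputs are a difference of 3.5 and an SD of 8 (Protocol 13.2) and a two-sided 5% level (SAP 7.5), with a paired t-test by the noncentral t. The plan states more than 90% for 40 participants; I get 77.0%. That is a separate matter, and the ratios in step 3 do not use it. With 50 recruited and no loss, power is 85.8%.

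| f | Removed | Kept, one unfit | Kept, two unfit |
|---|---|---|---|
| 4% (48 / 49 / 48.3 pairs) | 84.3% | 85.1% | 84.6% |
| 10% (45 / 47.5 / 45.8 pairs) | 81.9% | 84.0% | 82.6% |
| 20% (40 / 45 / 41.7 pairs) | 77.0% | 81.9% | 78.7% |

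Test versus a reference cream (difference 2, SD 3) stays above 98% in every case.

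**The case against.** The strongest reply is that the protocol leaves more room than its two-way rule suggests. Section 10.6 allows necessary medication with withdrawal only a possibility, and 9.6 makes withdrawal discretionary. The rule in 12.1.1 covers eczema, not every local reaction. The termination-page sentence is a form instruction and does not itself end visits, and the CRF is not available to check. All of this stands. A reader might infer that a flare, or treating it with TCS or TCI, forces the participant out, or that the text forbids later assessments. The documents support neither reading. What remains is that no section tells the investigator to keep the assessments.

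A second reply is that removing whole participants keeps the four areas balanced, which is defensible in a 31-day mechanistic study, and that 50 are recruited to leave 40. Balance is a real advantage, and area-level retention gives some of it up. The dropout allowance covers losses in number but does not justify avoidable ones.

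A third reply is that the gain is small, rests on an assumed frequency and misses the worst case. This also stands. Nothing is kept if the test-cream area is affected, test versus no treatment is rescued only when a reference-cream area is affected, and bias in contrasts that use the affected area remains.

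Finally, dropout analysis, disposition, discontinuations and AEs by test site are already planned (Protocol 13.1.2 and 13.1.9, SAP 7.4, 7.6 and 8). More tabulation alone would be reporting detail, so the case rests on the assessment rule.

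**Conclusion.** The point holds as a cheap improvement to the rules, not as a flaw that undermines the trial. For a participant whose cream is stopped, or who has one unfit area, the protocol neither requires nor rules out the Day 29 and Day 31 assessments. If the investigator removes the participant before Day 31, the primary value is lost at all four areas, although the planned random-subject model could use those that remain. The loss comes from the withdrawal wording and not from the analysis method. The FAS definition is unaffected, but its primary analysis can use only areas with both readings.

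Over an assumed 4–10% affected, retention limits the rise in each contrast's standard error to 1.0–2.6% instead of 2.1–5.4%, about 1 to 2 points of power for test versus no treatment. It saves less if the neighbouring area is also unfit. The 20% row is a ceiling in which every dropout has this single cause. All figures assume that the affected area is equally likely to be any of the four and that everyone counted in f would otherwise be removed. Selection is not quantified because the documents give no basis for it.

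**What to change.** **Protocol 9.6 and 12.1.1.**
- Separate stopping cream on, or treating, one or more areas (including the untreated one) from leaving the study, and complete the termination page only for the latter.
- Unless consent is withdrawn, keep the scheduled Day 29 and Day 31 assessments on every area the investigator judges fit.
- Whether to stop a cream, and whether an area is fit for the SLS patch, stay with the investigator.

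**SAP.**
- Analyse these areas in the FAS under the randomised treatment, in the planned model.
- Handle the stop, or any TCS/TCI use, in the PPS.
- Add a sensitivity analysis restricted to participants with all four areas.
- Count missing primary values by area, treatment and reason beside the planned disposition table.

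**Cost.** Wording in two protocol sections, one sensitivity analysis and one table, with no new visits or procedures. There are three downsides. Some FAS readings will come from areas with under 4 weeks of cream. Area-level missingness may depend on treatment, which is why the four-area analysis is included. Treatment put on one area may reach its neighbour on the same forearm, which cuts what is kept from 1/2 to 1/6 of affected participants per contrast.

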#### 9.7 Premature Termination of the Study

The Investigator or the Sponsor may terminate this study prematurely for any reasonable cause. The Independent Ethics Committee(s) (IECs) and Competent Authority(ies) (CAs) should be informed promptly.

Conditions that may warrant termination include, but are not limited to:

• The discovery of an unexpected, significant, or unacceptable risk to the participants enrolled in the study, or potential study participants

If the CA obtains information that raises doubts about the safety or scientific validity of the clinical study, the CA can suspend or prohibit the study. Before the CA reaches its decision, it shall, except where there is imminent risk, ask the Sponsor and/or the Investigator for their opinion, to be delivered within one week (Directive 2001/20/EC, Article 12, Section 1).

Confidential Page 33 of 65

Version: Version 3.0 Date: 15 August 2019 Sponsor: ACO Hud Nordic AB Study Code: Novum ACO-CT-2018-01 EudraCT No.: 2018-002945-12

If the study is prematurely terminated or suspended for any reason, the Investigator/institution should promptly inform the study participants and should assure appropriate therapy and follow-up for the participants.

#### 9.8 Remuneration

All participants enrolled onto the study will be compensated for their time. A payment in Amazon Vouchers will be made as follows:

• £100 for completing the study

This is based upon a rate of £20 per visit to our test site.

Participants who fail to complete the study, for whatever reason, may claim a proportion of the remuneration commensurate with the extent of their participation.

Travel to and from the test site by taxi will be additionally arranged at our expense (not taken out of the remuneration).

Confidential Page 34 of 65

Version: Version 3.0 Date: 15 August 2019

### 10 TREATMENT OF PARTICIPANTS

#### 10.1 Investigational Products

#### 10.1.1 Treatment Regimens

The participants will apply 3 different creams on their lower volar forearms and the treatment area will be randomized. One randomized area will be left untreated. One FTU of the creams will be applied twice daily for 28 (± 3 days).

Sponsor: ACO Hud Nordic AB

EudraCT No.: 2018-002945-12

Study Code: Novum ACO-CT-2018-01

#### 10.1.2 Identity of Investigational Products

The following creams will be used:

- Test cream: Miniderm Novum, moisturising cream containing 2% urea and 20% glycerol (no marketing authorization, Investigator's brochure provided with the protocol)
- Reference cream: Miniderm 20% cream, moisturising cream containing 20% glycerol (marketing authorization in Sweden, Norway and Finland, SmPC provided with the protocol)
- Reference cream: Diprobase cream (no pharmacologically active component), paraffin based cream (marketing authorization, SmPC provided with the protocol)

#### 10.1.3 Packaging and Labelling of Investigational Products

The test cream will be produced by Pharmavize NV [name].

Miniderm 20% cream will be produced by Medgenix Benelux, [name].

Miniderm Novum and Miniderm 20% cream will be filled in identical plastic tubes of 100 mL at Pharmavize.

Diprobase cream will be used in its original tube of 50 g and labelled as the other products.

The products will be labelled with:

- Name, address and telephone number of the sponsor
- pharmaceutical dosage form, route of administration, quantity of dosage units and the identifier of the product
- batch number
- trial reference code
- trial subject identification number
- name of Investigator

Confidential Page 35 of 65

Version: Version 3.0 Date: 15 August 2019

- name of Sponsor
- "directions for use, please see patient diary"
- "For clinical trial use only"
- Storage conditions
- Expiry date in month/year format
- "keep out of reach of children"
- Randomized application site (upper left arm, lower left arm, upper right arm or lower right arm)

Sponsor: ACO Hud Nordic AB

EudraCT No.: 2018-002945-12

Study Code: Novum ACO-CT-2018-01

#### 10.1.4 Storage and Handling of Investigational Products

All creams in the study should be stored in a locked cupboard below 25°C and out of reach of children. Temperature logs throughout the study will be kept. Only personnel authorised by the principal investigator should dispense the study medication, and the accountability is the responsibility of investigator. The investigator/study nurse/pharmacist must complete and return the study medication supply form verifying the receipt of study medication to the study monitor.

A study medication inventory (dispensing records) for all medication dispensed must be maintained at all times and always kept current.

For application of the creams, please refer to Section 10.4.

#### 10.2 Method of Assigning Participants to Treatment Groups

Randomisation (allocation of the treatments to the test sites) will be performed according to a randomisation list with balanced allocation to the 4 different test areas (to avoid site-dependent effects). Participants eligible for the study will be provided with a participant ID number at Visit 1.

#### 10.3 Selection of Doses in the Study

The doses of the creams will be 1 FTU of cream per treatment area.

#### 10.4 Selection and Timing of Dose for Each Participant

The creams should be applied morning and evening according to the randomisation for 28 days (± 3 days).

Confidential Page 36 of 65

Version: Version 3.0 Date: 15 August 2019

## 10.5 Blinding

The Investigator should keep the randomisation key and the numbering of the products in a secure, limited-access location to prevent inadvertent breaking of the blind. In an emergency requiring information about the study treatment, the appropriate envelope may be opened and the date, time and reason should be recorded and signed by the Investigator or his/her delegate. If the code should be broken without prior announcement to the Sponsor, the person who breaks the code should inform the Sponsor immediately.

Sponsor: ACO Hud Nordic AB

EudraCT No.: 2018-002945-12

Study Code: Novum ACO-CT-2018-01

Data will be collected and entered into the database on an ongoing basis. A clean file declaration will take place when all data have been entered and cleaned, and the database will then be locked before starting the analyses.

All study personnel at the clinic, as well as the CRO and Sponsor staff will remain blinded to the individual treatments during the study. Miniderm Novum and Miniderm will be packed in identical tubes and therefore blinded to both participants and study personnel. Diprobase cream will be provided in its original tube and thus not blinded. A product code will be indicated on the label to enable identification of the different treatments. The products are labelled upon arrival to the clinical research facility and therefore none of the study personnel can discriminate Miniderm Novum from Miniderm.

